Based on these assumptions and taking into consideration a potential drop-out rate of 5%, 254 patients (127 in each treatment arm) need to be enrolled in order to observe 192 events which should be sufficient to yield 80% power for a two-sided log-rank test at an overall alpha level of 5%.

In order to control the overall type one error at the 5% level, the interim analyses will follow a Lan-DeMets alpha spending approach, using an O'Brien-Fleming boundary function. According to this approach, the study will be stopped after 50% of the total number of events (96 events) due to efficacy (median survival in experimental arm greater than in the control arm) or due to futility (median survival in experimental arm less than in the control arm) at a 2-sided alpha = 0.00306.

Secondary endpoints

Time to distant progression (TTPd)

Time to treatment change due to systemic progression.

Time to local progression (TTPI)

Increase in size >25% of the primary tumor in arm B (no local therapy).
Local recurrence in arm A (local therapy).

For the secondary endpoint, TTPd and TTPI, the *2-sided log-rank test* (unstratified) will be used to test for differences between local versus no local therapy at an overall alpha level of 5%. A stratified version of the 2-sided log-rank test will be performed

with the stratification factors used for randomization except geographic region. Kaplan-Meier curves and estimates will be provided for each treatment group. The multiple analysis will be conducted with a *Cox regression model*. The local recurrence in arm A (local therapy) will be assessed with *univariate and multiple logistic regression analysis*.

Reduction of growth factors, circulating tumor cells, stem cells in pre-selected centers

For the secondary endpoint growth factors, circulating tumor cells, stem cells, post intervention measurements are compared with baseline values and tested with the *repeated measures ANOVA*. Correlations between initial or late drop of growth factors, circulating tumor cells, stem cells and median survival or TTP, respectively, will be calculated with the *Spearman rank order correlation test*. The stem cell and growth factors in the tumor will be correlated with the stem cell and growth factor release into the peripheral circulation and known prognostic factors such as her2neu expression and grading as well as survival time. The association with her2neu expression and grading and categorical variables will be assessed by an *ANOVA*. The association with the survival time will be analysed with a *Cox regression*.

Surgical Therapy

Local therapy consists of lumpectomy or mastectomy with a resection free margin of at least 1 mm or more demonstrated on paraffin embedded histological sections. Intraoperative frozen sections are allowed but not definitive for margin assessment. For axillary surgery, either axillary dissection level I and II or sentinel node biopsy has to be performed (mandatory) which has only to be followed by axillary dissection in case of macrometastasis of at least one sentinel lymph node.

Surgery on demand

In the arm B (no local therapy) it may be necessary to perform local therapy on demand (surgery, radiotherapy). Reasons may be uncontrolled bleeding or infected exulcerations with a septic component and no treatment benefit from conservative therapy. This will be considered as protocol deviation. However, the patient's follow up is recorded and data are available for retrospective analyses as intention to treat.

Radiation therapy

Local radiation therapy of the breast may be given according to center policy in therapy arm A. In arm B this will be considered as protocol deviation. Radiation therapy of the metastases is allowed according to center policy in both arms.

Systemic therapy

Chemotherapy or anti-hormone therapy is used according to center policy. The following recommendations should be followed:

1. In cases of radiotherapy and chemotherapy (arm A), radiotherapy should not be given later than 6 months after surgery. Radiotherapy is allowed in parallel to anti-hormonal treatment.
2. In premenopausal patients anti-hormonal treatment - if indicated - should always be coupled with ovarian ablation (surgical resection or systemic endocrine treatment, e.g. with goserelin) to ensure complete hormonal blockade.

3. In postmenopausal patients the primary anti-hormonal treatment - if indicated - should be an aromatase inhibitor (if there are no contraindications).
4. Chemotherapy – if indicated - should precede anti-hormonal treatment – if indicated.

Follow up (Appendix 4)

Routine laboratory tests for safety assessment of palliative systemic therapy and radiological follow up are performed according to the centers' guidelines with the recommended procedures as follows:

- Clinical examination and laboratory tests (red and white blood cells, Tumor marker CA15-3 and CEA) before and every 2-4 months after randomization. After two years examinations should be done every 5-7 months.
- CT scan of the liver and the lung before and every 2-4 months after randomization. Alternatively a PET-CT scan can be performed. Ultrasound of the liver or chest X-ray is only recommended in cases of contraindication for CT. After two years examinations should be done every 5-7 months.
- CT scan or alternatively PET-CT scan of bone metastases (if diagnosed) before and in case of pre-randomization diagnosed bone metastases every 2-4 months after randomization or in case of suspect new bone metastases anytime after randomisation for diagnostic imaging. After two years examinations should be done every 5-7 months.
- EORTC QLQ-C30 and QLQ-BR23 quality of life (Appendix 5) sheets before and every 6 months after treatment until 24 months visit, then every 12 months until 48 months visit.

Blood specimens in pre-selected centers (Appendix 6)

15ml of blood are drawn before surgery and 1-3 days after surgery (arm A only), as well as before first application of systemic therapy, 3-6 months and 12 months after first application of systemic therapy in arm A and arm B.

Tissue specimens in pre-selected centers

Tumor tissue from core needle biopsies before systemic therapy (arm B no local therapy group) or from surgical resections (arm A local therapy group) are used for further immunhistochemical and flow cytometry analyses. Only in pre-selected centers with experimental background.

Measurements of VEGF and TGF beta in pre-selected centers

Blood

Blood (7.5 ml) is drawn into pre-chilled CTAD-tubes, kept on ice and further processed within 30 min: After an initial centrifugation step at 1000 x g and 4°C for 10 min, plasma is transferred to microtubes and subjected to further centrifugation at 10000 x g and 4°C for 10 min (to remove “contaminating” platelets). The supernatant is stored in aliquots at -70°C to avoid repeated cycles of freezing / thawing prior to analysis. Samples are transported to the University of Vienna surgical research laboratories for further examinations immediately under dry ice. Plasma samples are

analyzed in duplicate by ELISA to determine the concentration of circulating angiogenic factors. Commercially available ELISA tests are applied for VEGF-A, -C, -D (Quantikine, R&D Systems, Minneapolis, MN) and TGF-beta,-beta 1,-beta 2 and -beta 3 (R&D System).

Tumor

Specimens from core needle biopsies (arm B) or surgical resected tumors (arm A) are fixed in formaldehyde and sent to the Medical University of Vienna together with the plasma samples. Thereafter blocks are stained with anti-VEGF and anti-TGF beta (R&D Systems) for immunhistochemistry and paraffin blocks are analysed.

Assessment of circulating tumor cells (CTC) and breast cancer stem cells in pre-selected centers

Blood

Peripheral blood (7.5 ml) will be drawn in EDTA-tubes to which a cell preservation solution is added. Probes are shipped to the Medical University of Vienna right away at 4°C. The cells are subjected to immunostaining with appropriate isotype controls or a set of antibodies for evaluation of CTCs (anti-human CK8⁺, 18⁺ and 19⁺ and CD45⁻) or breast cancer stem cells (anti-human ESA⁺ CD44⁺ CD24⁻ lineage⁻) within 72 hours. Lineage markers antibodies are anti-CD2, -CD3, -CD10, -CD16, -CD18, -CD31, -CD64, -CD140b. Samples will be analyzed with an EPICS XL-MCL flow cytometer and with acquisition of at least 100000 cells per sample to yield an informative number of events for CTCs (anti-human CK8⁺, 18⁺ and 19⁺ and CD45⁻) and endothelial progenitors (CD3⁻, CD19⁻, CD33⁻, KDR⁺, CD133⁺).

Tumor

Tumor specimens are minced and kept in RPMI medium 1640 under sterile conditions for a maximum of 72 hours. During that time, specimens are shipped to the Medical University of Vienna together with other specimens. Thereafter the tumor pieces are mixed with ultra-pure collagenase III in medium 199 and allowed to incubate at 37°C for 3-4 hours. After incubation, cells are filtered through a 46µl nylon mesh and washed with RPMI/20% FSB, then washed twice with HBSS. Cell are counted and transferred to a 5 ml tube, washed with HBSS and HICS and incubated with Sandoglobin solution for 10 min. After another washing step with HBSS and HICS, antibodies are added. The antibodies are the same as for blood specimen.

Stopping rules (End of Study)

1. Withdrawal of informed consent
2. Death
3. Lost to Follow Up

Risks and Benefits for the patients

Risk of biopsy

Core needle biopsies are routinely performed to preoperatively diagnose breast cancer. Morbidities are bleeding or infections which usually may be treated conservatively. Cell seeding has been demonstrated but the clinical impact is only minor²⁹.

Risk of blood withdraw

Usually there are no complications with venous blood withdraw, however, a thrombophlebitis or local pain and red skin may result from this invasive diagnostic procedure. The risk is between 1 and 5%. Local cooling packs and sometimes antibiotics and bandages may be necessary to reduce the pain and the infection.

Risks of local treatment

The main risk for the patient is for women in the treatment group A (local therapy) who undergo operation under general anesthesia. In general the local treatment (surgical removal of the primary tumor) has been done throughout more than 100 years in metastasized and non-metastasized patients with excellent results. Recently El-Tamer et al published morbidity and mortality rates of mastectomy and lumpectomy in 3107 patients³⁰.

30-day mortality was 0 – 0.24% and 30-day morbidity was between 1.8 and 5.7% showing higher numbers for mastectomized patients. The highest morbidity rate was due to superficial wound infections with 3% in the mastectomy group. Wound infection was associated with adipositas (BMI >30). Sever events such as cardiac arrest or pulmonalembolia were seen in 0.06% or 0.24%, respectively. Thrombophlebitis and systemic infections have been seen in 0.07 – 0.24% and 0.07 - 0.3%, respectively. Acute renal insufficiency has been observed in 0.06% of patients undergoing mastectomy.

Bleedings as well as seroma productions are rare and may be observed in 1 to 2% of patients. Most bleedings and hematoma formations may be treated conservatively while only a minority may need to undergo a second operation.

There is, however, a small risk to need a second operation due to positive resection margins. This risk is reduced by the use of intraoperativen frozen section analyses to 6% ([name] et al; data submitted).

Benefit for the patients

The benefit for the patient may be a 10% absolute increase in median survival from 24 to 36 months. More over if the hypothesis is true that the resection of the primary tumor in metastasized patients increases overall survival, the knowledge about carcinogenesis increases substantially. If we are able to demonstrate that circulating tumor cells and/or growth factors released from the primary tumor may be at least in part responsible for this improvement, the doors are open to investigate new therapeutic strategies in these patients such as anti-growth factor antibodies or systemic therapies destroying tumor stem cells. No trial has been published so far answering these important questions which may, in fact, guide us to new aspects of cancer therapy.

ADMINISTRATIVE REQUIREMENTS

Good Clinical Practice

- The study will be conducted in accordance with the International Conference on Harmonisation (ICH) for Good Clinical Practice (GCP) and the appropriate regulatory requirement(s). Essential clinical documents will be maintained to demonstrate the validity of the study and the integrity of the data collected.

Ethical Considerations

- The study will be conducted in accordance with ethical principles founded in the Declaration of Helsinki (see Appendix 5). The IEC will review all appropriate study documentation in order to safeguard the rights, safety and well-being of the patients.

Patient Information and Informed Consent

The principal investigators at each center will ensure that the patient is given full and adequate oral and written information about the nature, purpose, possible risk and benefit of the study. Patients must also be notified that they are free to discontinue from the study at any time. The patient should be given the opportunity to ask questions and allowed time to consider the information provided.

The patient's signed and dated informed consent must be obtained prior to undertaking any trial-related procedure which is not part of the routine clinical management of the patient (i.e. would not be indicated outside the study).

Additionally all consent forms have to be signed and dated by the investigator or authorised delegate. If the patient is unable to read or write, the consent forms should be signed and dated by the investigator and an independent witness, to indicate that the patient apparently understood the information and consented freely.

The written subject information must not be changed without prior release by ABCSG and the approval by IRB/IEC.

The principal investigator(s) must store the original, signed Informed Consent Form. A copy of the signed Informed Consent Form must be given to the patient.

Patient data protection

The Informed Consent Form will incorporate wording that complies with relevant data protection and privacy legislation. Pursuant to this wording, patients will authorise the collection, use and disclosure of their study data by the Investigator and by those persons who need that information for the purposes of the study.

The Informed Consent Form will explain that study data will be stored electronically, maintaining confidentiality in accordance with national data legislation. All data computer processed by ABCSG will be identified by randomization code / study code.

The Informed Consent Form will also explain that for data verification purposes, authorized representatives of ABCSG, a regulatory authority, an IEC may require direct access to parts of the hospital or practice records relevant to the study, including patients' medical history.

Data management

Data management is carried out by ABCSG by the use of the MACRO, InferMed's web based electronic data collection system for clinical trials. MACRO has been designed to support the requirements of internationally recognised ICH Good Clinical Practice and FDA 21 CFR Part 11.

On-site Monitoring

The ABCSG Monitor is responsible for verifying the CRFs at regular intervals throughout the study to verify adherence to the protocol, completeness, accuracy and consistency of the data and adherence to local regulations on the conduct of clinical research. The monitor should have access to subject medical records and other study-related records needed to verify the entries in the eCRF.

[figure not shown]
Publication Policy

Authorship of any publications resulting from this study will be determined on the basis of the Uniform Requirement for Manuscripts Submitted to Biomedical Journals (International Committee of Medical Journal Editors, 2004), which states:

- Authorship credit should be based on (1) substantial contributions to conception and design, acquisition of data, or analysis and interpretation of data; (2) drafting the article or revising it critically for important intellectual content; (3) final approval of the version to be published. Authors should meet conditions 1, 2, and 3.
- When a large, multicenter group has conducted the work, the group should identify the individuals who accept direct responsibility for the manuscript. These individuals should fully meet the criteria for authorship defined above.
- Acquisition of funding, collection of data, or general supervision of the research group, alone, does not justify authorship.
- All persons designated as authors should qualify for authorship, and all those who qualify should be listed.
- Each author should have participated sufficiently in the work to take public responsibility for appropriate portions of the content.

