Additional we measure circulating tumor cells and growth factors in the peripheral blood at pre-selected centers. Therefore 15ml of blood are drawn before surgery and 1-3 days after surgery (arm A only), as well as before first application of systemic therapy, 3-6 months and 12 months after first application of systemic therapy in both arms.

Quality of life questionnaires are handed out to all patients before surgery or first application of systemic therapy as well as every 6 months after enrollment until 42 months visit.

Inclusion and Exclusion Criteria

Females whose conditions satisfy all of the following criteria are the only patients eligible for this study.

General inclusion criteria

1. Written informed consent must be obtained and documented prior to beginning any protocol specific procedures and according to local regulatory requirements.
2. Patients age ≥ 18 years
3. Eastern Cooperative Oncology Group Performance Status is 0 -2 (Appendix 3)
4. Able to comply with the protocol requirements during the treatment and follow-up period.

Disease specific inclusion criteria

5. Untreated synchronous metastasized invasive carcinoma of the breast with the primary tumor in situ (bilateral synchronous metastasized breast cancer patients are eligible).

6. The primary tumor must be identified and may be any size, however, primary resection with resection free margins must be possible.
7. Invasive adenocarcinoma of the breast on histological examination.
8. The metastatic site must be identified by radiological assessment (Computer Tomography of the chest and the abdomen OR ultrasound and chest x ray for visceral metastases; bone scan AND/OR computer tomography AND/OR magnetic resonance for bone metastases). A biopsy is not necessary.

Exclusion criteria

1. Patients in whom a R0 resection (microscopic free margins) is clinically questionable
2. Inflammatory cancer
3. Patients with brain metastases
4. Patients who are not eligible for general anesthesia and operations
5. Patients without metastatic breast cancer (patients with a tumor marker value (CEA, CA15-3) above normal levels without the radiological proven evidence of metastases are not eligible for the study)
6. Patients with a second untreated malignancy
7. Any previous malignancy treated with curative intent and the patient has not been disease-free for 5 years – exceptions are:
 - a. carcinoma in situ of the cervix
 - b. squamous carcinoma of the skin
 - c. basal cell carcinoma of the skin

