2.2.2. Secondary objectives

The secondary study objectives are

1. to investigate the role of the primary breast cancer resection in terms of local and distant time to progression
2. to evaluate the role of peripheral circulating tumor cells and growth factors in synchronous metastasized breast cancer patients and whether there is any association between their detection and the median survival in pre-selected centers
3. to examine whether the resection of the primary breast cancer influences peripheral circulating tumor cells and growth factors in pre-selected centers
4. to investigate the quality of life (QoL) in both groups

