3.6.2. Data set for secondary endpoints

Data analysis for the secondary endpoint time to distant progression and time to local progression will be based on the ITT-population.

Data from QoL questionnaires will be analyzed for all the patients which filled baseline or at least on after baseline questionnaire.

Reduction of growth factors, circulating tumor cells, stem cells will be analyzed on all evaluable data from pre-selected centers.

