3.6.3. Efficacy analyses for secondary endpoints

Difference in time to distant progression and time to local progression between local therapy versus no local therapy will be estimated through 2-sided log-rank

With respect to analysis of QoL endpoints the mean change of the linear transformed scores from baseline (and 95% CI using the normal approximation) will also be assessed. Line charts depicting the mean changes (and standard errors) of items and subscales over time will be provided for each treatment arm from the baseline assessment.

Completion and compliance rates will be summarized at each time point by treatment arm with reasons for missing data.

Reduction of growth factors, circulating tumor cells, stem cells in pre-selected centers will be defined in later version of SAP in an efficient amount of data will be available.

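### The only stated method linking blood-marker drop to survival or progression is Spearman correlation, which cannot handle censoring; the SAP postpones this analysis without replacing the method

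*Protocol*

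**What the plan says.** **Method.** The protocol's outcome section, under the reduction of growth factors, circulating tumor cells and stem cells, plans "Correlations between initial or late drop of growth factors, circulating tumor cells, stem cells and median survival or TTP, respectively", using the "Spearman rank order correlation test". Median survival is a group summary that cannot be ranked patient by patient, so individual survival time must be meant.

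Later in the same paragraph the text turns to markers in the tumor and says "The association with the survival time will be analysed with a" Cox regression. By its position, that sentence covers tissue markers, not the drop in blood markers.

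**Sampling.** Protocol, Study design: blood is taken before surgery and "1-3 days after surgery (arm A only"), before first systemic therapy, and "3-6 months and 12 months after first application of systemic therapy in both arms".

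**SAP.** Section 2.2.2 keeps the objective, asking "whether there is any association between their detection and the median survival in pre-selected centers". Section 3.6.2 says the marker data "will be analyzed on all evaluable data from pre-selected centers". Section 3.6.3 says the analysis "will be defined in later version of SAP", if enough data become available. Section 4 lists no marker table. Section 5, on changes from the protocol, mentions only center in place of geographic region.

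**Censoring.** The protocol's primary-endpoint section and SAP 3.3.1, 3.5.1 and 3.5.2 censor patients who are alive at the end or leave early. Both progression endpoints are analysed by log-rank test.

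**The concern.** Spearman needs a complete rank for every patient, and a censored survival time has none. An analyst must either rank the censoring time as if it were a death or drop the patient. The plan does not choose, and the two choices give very different answers.

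The arms are a second gap. The trial hypothesises that surgery both lowers the markers and prolongs survival. If so, a correlation over pooled arms can appear with no marker–survival link inside either arm. That would seem to support the protocol's second hypothesis, that reduced circulating cells and factors explain the survival gain, when it shows only the arm effect.

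At stake are secondary objective 2 and that mechanistic claim, not the primary comparison.

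**Working it through.** **1. Inputs from the documents.** Medians 36 (A) and 24 (B) months, HR 0.666, 127 patients per arm, 48 months accrual, 108 months in total, 192 events, possible stop at 96 events, 5% drop-out.

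**2. The plan's event figure.** Schoenfeld: 4 × (1.960 + 0.842)² / (ln 0.666)² = 31.40 / 0.1652 = 190.03, so 191 events; Freedman gives 196. Power at 192 events is 80.4%. The stated 192 is sound.

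**3. How much censoring.** With exponential survival and uniform accrual, the probability of observed death by month 108 is 1 − [exp(−60λ) − exp(−108λ)] / (48λ), with λ = ln 2 / median.

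- B: 1 − (0.1768 − 0.0442) / 1.3863 = 0.904
- A: 1 − (0.3150 − 0.1250) / 0.9242 = 0.794
- Deaths: 127 × (0.904 + 0.794) = 215.7, so (254 − 215.7) / 254 = 15% censored
- At 192 deaths (expected month 86.6): 62 / 254 = 24%
- At 96 deaths (month 46.2, about 244 enrolled): 148 / 244 = 61%

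**4. Effect on the correlation.** The documents give no marker sample size or effect, so these are assumptions: first systemic therapy at month 2 (A) and 0.5 (B), the sample 12 months later, and full-follow-up rho about 0.38. Two data models were simulated with 400,000 patients each: proportional hazards with log-HR 0.5 per SD, and a normal copula.

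| Step | Proportional hazards | Copula |
|---|---|---|
| Full follow-up, all patients | 0.38 | 0.37–0.38 |
| Alive at the sample, no censoring | 0.36 | 0.27 |
| Month 108, censored times ranked | 0.33 | 0.26 |
| 192 deaths, censored times ranked | 0.30 | 0.24 |
| 96 deaths, censored times ranked | 0.14 | 0.12 |

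Using deaths only, across both models: 0.19–0.20 at month 108, 0.15–0.17 at 192 deaths, 0.08–0.10 at 96 deaths.

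At month 108, ranking censored times costs 0.27 − 0.26 = 0.01 (copula) to 0.36 − 0.33 = 0.03 (proportional hazards, with 5% drop-out). Without drop-out the cost is 0.01–0.02.

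A simpler case without survivor selection (n = 100, marker HR 1.5 per SD) agrees. Rho falls from 0.31 to 0.30 at 15% censoring and 0.29 at 26% when censored times are ranked, but to 0.19 and 0.16 when only deaths are used.

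**5. Power** (proportional-hazards model, 12-month sample):

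| Cut-off, n | Spearman, ranked | Spearman, deaths only | Arm-adjusted landmark Cox |
|---|---|---|---|
| Month 108, 60 | 58% | 18% | 72% |
| Month 108, 120 | 88% | 35% | 95% |
| 192 deaths, 60 | 47% | 11% | 63% |
| 192 deaths, 120 | 79% | 20% | 91% |

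Spearman on uncensored times at month 108, n = 60, has 66%.

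**6. Pooled arms.** Assume no link within either arm and a 12-month drop larger in arm A by 0.5, 1 or 2 SD. Pooled Spearman shows a false rho of 0.04, 0.08 or 0.14. It is significant in 5%, 9% or 15% of trials at n = 60, and in 7%, 12% or 26% at n = 120. Arm-adjusted landmark Cox stays at 5–7%.

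**The case against.** **The method is already reopened.** SAP 3.6.3 postpones the analysis, conditional on data, and no marker table is planned. Silence in section 5 is weak evidence that Spearman is retained, because a postponed analysis is not yet a change. This stands in part: a reader might infer that the SAP adopts Spearman, and it does not. But it names nothing else, so the protocol's method is the default until that section is written.

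**Censoring itself may do little harm.** This stands where censored times are ranked with full follow-up. A reader might blame censoring for the whole fall from 0.38 to 0.26–0.33. Most of the low end is survivor selection, which landmark Cox shares. Of the gap between 72% and about 59% power at n = 60, 66 − 59 = 7 points are censoring; the other 72 − 66 = 6 reflect arm adjustment and a data model that favours Cox. The 96-death figures apply only if the interim boundary is crossed, since SAP 3.2.1 times the primary analysis after the last patient's last visit.

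**Deaths before a sample are not ignored.** SAP 3.1.2.1 (only evaluable measurements, no imputation), read with 3.6.2, implies that patients without a sample are left out. This stands.

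**A related inference the documents do not support.** SAP 3.9 lists endocrine therapy, chemotherapy and immunotherapy as candidate covariates, and SAP 3.1.3 bases covariate analyses on actual values. A reader might infer that the Cox models adjust for therapy received after randomisation. However, the stratification factor in SAP 2.3 is planned therapy, SAP 3.8 groups first-line therapy with strata and screening factors, the eCRF footnote in 3.9 is not attached to the therapy items, and 3.1.3 contrasts the eCRF with the randomisation system. This is an unlabelled item, not a wrong rule. Material bias in the arm effect would also need assumed unequal uptake and late starts.

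**Conclusion.** The concern holds for the marker analysis. Spearman is unsuited to these censored outcomes, no document withdraws it, and the handling of arms is unstated.

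The loss is small at month 108 if censored times are ranked (0.01–0.03 in rho). It is substantial if only deaths are used (rho 0.19–0.20; power 18% against 72% at n = 60) or if the data are cut earlier. No document states which coding would be used. Pooling can raise the false-positive rate to 26% in the most extreme case examined.

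All these sizes rest on assumed marker effects, marker sample sizes and therapy start times. The censoring fractions rest only on the plan's own design figures and exponential survival. The primary unstratified log-rank test is not affected. The change should be made when SAP 3.6.3 is written.

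**What to change.** In the completed SAP 3.6.3:

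- Replace Spearman with Cox regression from a landmark at the sample date, or with the marker as a time-dependent covariate, adjusted for arm.
- Fit the 1–3-day post-surgery sample within arm A only, where it is taken.
- Report by arm how many patients died or were censored before each sample.
- Record the replacement in section 5 as a change from the protocol.

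This is a wording change that needs no new data. Its downside is that patients who die or are censored before the sample are excluded, as SAP 3.1.2.1 and 3.6.2 already imply. Under the design medians, 1 − 2^(−12/36) = 21% (A) and 1 − 2^(−12/24) = 29% (B) die within 12 months of randomisation. With the assumed therapy start times, about 28% are excluded at the 12-month sample and 10–18% at the 3–6-month sample. The landmark makes this selection explicit but does not remove it.

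**Minor clarification.** Add one sentence to SAP 3.9 and 3.1.3: the therapy covariates, and the actual value of planned first-line therapy, mean the plan at randomisation and not therapy later received. An ever-received flag would bring immortal-time bias into the sensitivity and exploratory Cox tables. With an assumed 60% uptake in both arms and mean start at 1, 3, 6 or 12 months, a therapy with no effect would show an OS hazard ratio of 0.94, 0.84, 0.72 or 0.61. Removing the therapy candidates or adding a time-dependent therapy table is optional.
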